**TABLE 5 - ASSIGNING TYPE OF AE THROUGH CAUSALITY**

Relationship to study product classified as:

[figure not shown]
Relationship	Description	AE Type
Unrelated	There is no evidence of any causal relationship	Unrelated AE
Unlikely	There is little evidence to suggest that there is a causal relationship (for example, the event did not occur within a reasonable time after administration of the trial medication). There is another reasonable explanation for the event (for example, the patient's clinical condition, other concomitant treatment).	Unrelated AE
Possible	There is some evidence to suggest a causal relationship (for example, because the event occurs within a reasonable time after administration of the trial medication). However, the influence of other factors may have contributed to the event (for example, the patient's clinical condition, other concomitant treatments).	AR
Probable	There is evidence to suggest a causal relationship and the influence of other factors is unlikely.	AR
Definitely	There is clear evidence to suggest a causal relationship and other possible contributing factors can be ruled out.	AR

### 13.3.4 REFERENCE SAFETY INFORMATION AND EXPECTEDNESS OF SARs

If there is at least a possible causal relationship of a SAR with an IMP, the investigator must assess the expectedness of the event. An unexpected adverse reaction is one not previously listed in the reference safety information (RSI) in the current Investigator Brochure (IB) or one that is listed but is more frequent or more severe than stated in the RSI.

## 13.4 SAFETY REPORTING FLOWCHART

Figure 1: Safety Reporting Flowchart

## 14 STATISTICAL CONSIDERATIONS

### 14.1 METHOD OF RANDOMISATION

The first 6 participants successfully enrolled into the trial will be sequentially pre-allocated to treatment groups B, C, D, F, G and H.

Participants thereafter will be block-randomised centrally using a computer-generated algorithm with a back-up manual procedure. Randomisation will be stratified on the basis of gender.

### 14.2 OUTCOME MEASURES

#### 14.2.1 PRIMARY ENDPOINTS

##### *Immunogenicity*

Antigen specific mucosal (cervico-vaginal for women, semen for men, and rectal and nasal for all) antibody ( $\mu\text{g}/\text{ml}$ ) responses two weeks after the final immunisation.

##### *Safety and Tolerability:*

- Proportion of participants with severe or greater (Grades 3-4) adverse reactions during the study
- Proportion of participants with vaccine-related serious adverse events (SAEs) throughout the study period

#### 14.2.2 SECONDARY ENDPOINTS

##### *Immunogenicity:*

To assess the kinetics of immune responses elicited by each of the vaccine regimens:

- Frequency of serum and mucosal binding antibodies to HIV CN54gp140 antigen measured by binding ELISA.

#### 14.2.3 EXPLORATORY ENDPOINTS

##### *Immunogenicity:*

- Frequency and magnitude of HIV-gp140 specific B-cell-mediated responses in the systemic compartment measured by B-cell ELISPOT.
- Frequency, titer and avidity of serum binding antibodies to other HIV Env antigens (alternative clades) by ELISA or other assays.
- Frequency and titer of serum neutralising antibodies to homologous virus, and, if warranted a wider a panel of viruses representing different clades.

- Longevity of serum and mucosal responses at 12 months following final immunization
- Frequency and magnitude of HIV-specific T-cell mediated responses measured by T-cell and ICS (Intracellular Cytokine Staining).
- PBMC ex-vivo HIV susceptibility assay
- Measurement of CN54gp140 serum IgA responses over time
- Frequency and magnitude of T-cell chemokine and cytokine release following ex-vivo antigen stimulation quantified by Luminex.
- Epitope mapping of B- and T-cell responses
- Serum antibody responses to Ad4-EnvCN54 and MVA-CN54 as a marker of anti-vector immunity and vaccine “take”
- Ex vivo analysis of colorectal biopsies for activation markers by ICS (Part 2 only)
- Susceptibility of rectal biopsies to HIV-infection – infection assays
- Durability of responses will also be determined by measurement of response at weeks 26 (visit 9) and 48 (visit 11) of the trial schedule

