Group selection	
Part 1:
 
Participants will be recruited and randomised into groups A-H with an oral and I.M placebo control (dependent on treatment allocation). This will be a participant blinded study where the participants are blinded to the group and dosing regime to which they are assigned. The laboratory undertaking immunological analysis will also be blinded to group and dosing regimen to prevent bias in analysis.
 
Part 2:
 
Participants will be randomised to the groups chosen for expansion. If only one group is expanded, there will be no randomisation. Participants will be blind to the vaccine regime group to which they have been assigned. The laboratory undertaking immunological analysis will also be blinded to group and dosing regimen to prevent bias in analysis.

Summary Information Type	Summary Details
Number of Participants to be Studied	
The study will enrol 48 participants to Part 1 and 12 participants for Part 2.
 
In Part 1, n=6 participants per group will be randomised to groups A-H.
 
In Part 2, n=6 participants will be vaccinated to the best responding regimes.
 
Recruitment will select potential participants who are willing to undergo serial

	blood draws. Additional participants may be enrolled to replace any early withdrawals.
Duration of Study Participation	Participants will be screened up to 90 days before the first vaccination and will be followed up for 24 weeks after the last vaccine administration. Excluding screening, participants will attend for 11 visits in 48 weeks.
Evaluation for Inter-Current HIV Infections	Participants will be tested for HIV according to the Trial Assessment Schedule (Table 2). Test results will be interpreted according to a pre-determined diagnostic algorithm. Should one or more serological HIV test(s) post-vaccination be positive, a nucleic-acid-based HIV test will be performed (if clinically indicated) to distinguish a true HIV infection acquired through exposure in the community from HIV seropositivity due to the vaccine-induced antibody response. HIV testing at additional time points may be performed upon request of the volunteer and Principal Investigator or designee as medical or social circumstances warrant.
Organisation	The Coordinating Center will be the Group of Mucosal Infection & Immunity at ICL. Drafting of the SAP will be lead by the Surrey Clinical Research Centre.

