#### 12.2 VACCINATION AND FOLLOW-UP VISITS

- The assessments that will be performed at each visit are described in Table 2.
- Participants will be required to make 11 scheduled outpatient visits over the course of 48 weeks. Time 0 will start on the day of enrolment, which is also the day of randomisation and the first immunisation, and must be within 90 days after screening.
- Vaccinations will take place at Weeks 0 (Month 0), 12 (Month 3) and 24 (Month 6).
- Serum and peripheral blood mononuclear cells (PBMC) will be collected for immunogenicity at Weeks 0 (enrolment), 4, 12, 16, 24, 25, 26, 28 and 48.
- Adverse events will be assessed during the enrolment visit before and after immunisations and at every visit thereafter until the final safety visit at Week 28; thereafter only serious adverse events will be recorded.
- Injection sites will be inspected vaccination days at Weeks 12 and 24 (pre-dose and 60 (+/-10) min post-dose), and at Weeks 13 and 25.
- Symptom-directed physical examinations will be done at Week 0 and at every visit thereafter until the final safety visit at Week 28.
- Vital signs will be done on vaccination days (pre-dose and 60 (+/-10) min post-dose) and at Weeks 1, 13, 25, 26 and 28.
- Concomitant medications will be collected at every visit up to the final safety safety visit.
- Blood for routine laboratory safety parameters will be collected at Weeks 0 (enrolment), 1, 12, 13, 24, 25, 26 and 28 and at any other visit if clinically indicated.
- Mucosal samples for antibody responses (genital / rectal / nasal) will be collected at Weeks 0, 4, 12, 16, 24, 26 and 48.
- Urine pregnancy test will be assessed at Weeks 0, 12, 24 and 28.
- Rectal swabs for Ad4-EnvCN54 PCR will be assessed at Weeks 0, 1, 4, 13, 16, 25, 26, 28 and 48.

- Rectal biopsies will be assessed at Weeks 0, 26 and 48 for participants in **Part 2** of the clinical trial only. Participants may opt out of this procedure.

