### 12.2.2 VISIT WINDOWS

The second and third vaccination visits scheduled for weeks 12 and 24 will be compliant with the protocol if they take place -7 / +14 days either side of the target date determined by the date of the previous vaccination. If there is a delay >4 weeks a decision will be made by the TMG (see **section 20.1**) as to whether immunisation will continue.

The post-immunisation safety visits scheduled for weeks 1, 13 and 25 will be compliant with the protocol if they take place +/- 1 day of the target date determined by the date of the previous vaccination.

The primary endpoint visit (Visit 9; Week 26) and final safety visit scheduled for week 28 will be compliant with the protocol if they take place  $\pm$  2 days either side of the target date determined by the date of the third vaccination. The follow-up visit at Week 48 will be compliant with the protocol if it takes place  $\pm$ 14 days either side of the target date determined by the date of the third vaccination.

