12.3 Secondary Endpoint Analysis

The secondary endpoints are related to the systemic responses which are based on serum antibody levels as specified in section 10.2. They will be analysed in the same way as the primary endpoint described in section 12.2.1 and 12.2.2. The same approach is used in both part 1 and part 2.

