12.4 Exploratory Endpoint Analysis

The exploratory analyses entail a wide range of laboratory analysis and procedures including ELISA, ICS, ELISPOT, Luminex and the likes, resulting with either a continuous outcome or binary outcome variable. The same approach is used in both part 1 and part 2.

All exploratory endpoints specified in section 10.3 will be analysed as per the primary endpoint as described in section 12.2.1 and 12.2.2.

13 Summary Statistics

Summary statistics of responses measured at multiple time points will be reported by each time point separately as well as all time points combined. These summaries will be classified by group and by gender within each group.

- Mucosal CN54gp140-specific antibody responses (IgA & IgG)
- Systemic CN54gp140-specific antibody responses (IgA & IgG)
- HIV-gp140 specific B-cell-mediated responses
- Serum binding antibodies to other HIV Env antigens
- Serum neutralising antibodies to homologous virus
- HIV-specific T-cell mediated responses
- T-cell chemokine and cytokine release
- Colorectal biopsies (Part 2 only)

and other responses related to exploratory outcomes

The frequencies and percentages of each of the responses listed above will also be reported.

Summary statistics of variables taken the screening will be reported separately by group, and by groups combined.

- Demographic information such as age and ethnic origin
- The general physical examination measured weight (kg), height (cm), BMI, temperature, blood pressure and heart rate (vital signs), inspection of the skin and respiratory, cardio-vascular, abdominal, and neurological systems

Continuous variables are summarised by a measure of central tendency (mean/median) and a measure of spread (standard deviation / range /Inter Quartile Range) depending on the skewness of the data.

Categorical variables are summarised by frequencies and percentages.

For each variable analysed, a boxplot will be produced to graphically illustrate the differences between groups, in terms of the medians, range, interquartile range. Boxplots will also highlight the outliers.

14 Multiplicity

The results presented will not be adjusted for multiplicity accounting for comparison of multiple outcomes. However, multi-group comparisons in part 1 will be adjusted for pairwise comparisons following a significant omnibus test.

15 Missing data

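### Longevity is defined at 12 months after the last dose, but the design stops sampling 24 weeks after it; separately, no planned analysis distinguishes slower decay from a higher peak

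*Protocol*

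**What the plan says.** The exploratory endpoint "Longevity of serum and mucosal responses at 12 months following final immunization" appears in identical form in Protocol section 2, Protocol 14.2.3 and SAP 10.3. Elsewhere the protocol describes a shorter horizon:

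- Under Duration of Study Participation in section 2, participants "will be followed up for 24 weeks after the last vaccine administration".
- Protocol 12.2 places the three vaccinations at Weeks 0, 12 and 24. Mucosal samples "will be collected at Weeks 0, 4, 12, 16, 24, 26 and 48", and serum and PBMC "will be collected for immunogenicity at Weeks 0 (enrolment), 4, 12, 16, 24, 25, 26, 28 and 48".
- Protocol 12.2.2: "The follow-up visit at Week 48 will be compliant with the protocol if it takes place" within 14 days either side of a target counted from the third vaccination.
- Protocol 12.9 closes the trial after Visit 11 (Week 48).
- The last bullet of the same endpoint lists sets durability at Weeks 26 and 48.

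On analysis, SAP 12.4 states: "All exploratory endpoints specified in section 10.3 will be analysed as per the primary endpoint as described in section 12.2.1 and 12.2.2". Section 12.2.1 gives responder proportions per visit and group, Fisher's exact test, Kruskal-Wallis with post-hoc comparisons in Part 1, and a mixed model with arm and gender in Part 2. SAP 12.1 and 13 add titres and summaries by visit. The hypothesis (Protocol 7.3.5.1, SAP 8) is that Ad4 priming improves both the size and the durability of the antibody response.

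**The concern.** The endpoint names a time at which nobody is sampled. The SAP carries the wording over unchanged, so nothing downstream corrects it. A report that followed the endpoint list would put a 12-month label on 24-week data. That label matters here because Protocol 7.1 treats the Thai efficacy trial (RV144) as the benchmark and describes it by its 12-month and 36-month results, with protection waning alongside systemic antibody. A mislabelled horizon invites a comparison that the data cannot bear.

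The second issue is narrower. Durability is part of the hypothesis, yet no method in SAP 12.2 to 12.4 contains visit, change from Week 26, or a group-by-visit term. The random participant effect in Part 2 does not help: the example table for that analysis uses Week 26 only, and the model statement has no time term. A Week 48 comparison of levels mixes how high a group peaked with how slowly it declined.

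**Working it through.** **Inputs.** Third vaccination: Day 168, labelled M6. Last visit: Day 336, labelled M12. Both are in Protocol section 4, Table 2. Window for the last visit: ±14 days from the third vaccination (Protocol 12.2.2).

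**1. The protocol's own follow-up figure.** 336 − 168 = 168 days; 168/7 = 24.0 weeks. This reproduces the stated 24 weeks. In calendar months, 168/30.4375 = 5.5.

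**2. Effect of the windows.** (168 − 14)/7 = 22 weeks and (168 + 14)/7 = 26 weeks, so at most 182/30.4375 = 6.0 months. A shifted third dose changes nothing, because Table 2 footnote 1 moves later visits by the same number of days. Even the widest window in the schedule, +56 days for the optional Part 2 biopsy, reaches only (168 + 56)/7 = 32 weeks.

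**3. Against the stated endpoint.** 168/365 = 46%. Twelve months after the last dose is Day 168 + 365 = 533, or Week 76.1. The shortfall is 365 − 168 = 197 days = 28.1 weeks (183/7 = 26.1 to 211/7 = 30.1 with the window).

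**4. Likely source.** The month labels in Table 2 fit 28-day months: 84/28 = 3, 168/28 = 6, 336/28 = 12. Week 48 is thus month 12 from the first dose and month 12 − 6 = 6 from the last. Even on 28-day months, 12 months after the last dose would be Day 168 + 336 = 504 (Week 72), 24 weeks after the final visit. Study time appears to have been tied to the wrong dose.

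**5. Peak against decay (hypothetical values).** Let two groups have Week 26 levels of 2 and 1, and let both retain a fraction f by Week 48. The Week 48 levels are 2f and f, a 2-fold difference. The Week 48/Week 26 ratio is f in both, so the groups differ by a factor of f/f = 1.0. The level test sees a difference; the ratio correctly shows none in decay. The interval covered is (336 − 182)/7 = 22 weeks.

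**6. Does the ratio gain power?** The documents give no SD, effect size or correlation. Assume two-sided 5%, 80% power, equal SDs, two equal groups and a normal approximation. The detectable difference in Week 48 level is (1.960 + 0.842) × √(2/n): 1.62 SD at n = 6 and 1.14 SD at n = 12. For the change, multiply by √(2(1 − ρ)), where ρ is the within-participant correlation:

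- ρ = 0.3: 1.91 SD (n = 6) and 1.35 SD (n = 12)
- ρ = 0.5: 1.62 and 1.14 SD, the same as for levels
- ρ = 0.8: 1.02 and 0.72 SD

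The ratio is more sensitive only if ρ exceeds 0.5. The reason to report it is that it targets decay.

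**The case against.** The date arithmetic is not in dispute. The case against reading more into it is strong, and most of it stands.

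- A reader might infer that the SAP uses only Week 26 methods. It does not. SAP 12.2.1 reports responder proportions with confidence intervals at every visit, SAP 12.1 describes titres by visit with rank tests where appropriate, SAP 13 summarises serum and mucosal IgG and IgA by visit, and the table shells run to Week 48. Read literally, SAP 12.4 also permits a between-group test at Week 48.
- A reader might infer from SAP 12.3 ("The secondary endpoints are related to the systemic responses which are based on serum antibody levels") that mucosal antibody has been dropped from the secondary endpoint. SAP 10.2.1 keeps it, section 12.3 refers back to 10.2, and 12.2.1 already gives mucosal responders by visit.
- A reader might infer that the 12-month slip is why durability goes untested. The hypothesis names no horizon, so the two points are separate.
- The level or responder proportion retained at Week 48 is itself a legitimate measure of durability, and the documents do not commit to decay rate. It would be too strong to say that such a comparison cannot show durability.
- A ratio test applied to everyone would be unsafe at mucosal sites. Concentrations are determined only in samples found positive (Protocol 14.5.2, SAP 12.1), and no mucosal response is expected in group A (Protocol sections 2 and 7.6). Placebo-primed ratios would be undefined or, if values were set to the cut-off, exactly 1.0, so non-responders would look perfectly durable.
- A parametric group-by-visit model is also tempting, but 8 groups × 7 mucosal visits is 56 cell means from 48 participants. It would run against the SAP's own reason for rank methods at n = 6.

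A misreport is also made less likely by the Week 26 and 48 bullet in the same lists and by the stated 24-week follow-up. That softens the consequence; it does not make the endpoint text correct.

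**Conclusion.** The endpoint as written cannot be delivered. The design gives 24 weeks after the last dose (22 to 26 with the window), 46% of the stated year, and no window closes the gap. This rests only on the visit schedule and needs no outside assumption. That week 48 was mistaken for 12 months after the last dose is an inference from the M12 label, but the correction does not depend on it.

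The analysis point holds in a limited form: visit-by-visit reporting and a Week 48 comparison are available, but nothing within participants or by group over time is planned, so equal decay from a higher peak could be read as durability. The 2-fold example is algebra, not trial data. These are exploratory and secondary matters in a Phase I trial that disclaims confidence about group differences (Protocol 14.3).

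**What to change.** **Wording.** In Protocol section 2, Protocol 14.2.3 and SAP 10.3, restate the longevity endpoint as: 24 weeks after the final immunisation (study week 48). If the protocol can no longer be amended, revise the SAP and label the results that way in the report.

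**Optional exploratory addition to the SAP.**

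- Serum: report each participant's log10 ratio of Week 48 to Week 26.
- Mucosal sites: report the same ratio only among participants positive at Week 26, with a stated rule for Week 48 values below the cut-off and a note that this is a subset defined after randomisation.
- Compare Ad4-primed (B–D, F–H) with placebo-primed (A, E) groups by a rank test stratified by arm, such as van Elteren. If group A has no mucosal responders at a site, as anticipated, the Arm 1 stratum contributes nothing there and should be described only.
- Present the ratios beside the Week 48 levels, not in place of them.

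**Cost.** A text change in three places and one small family of analyses (serum and four mucosal sites, IgG and IgA) on samples already scheduled, plus the below-cut-off rule. No visit, procedure or participant is added. The price is that the stated persistence horizon becomes shorter.

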### 14.3 SAMPLE SIZE

It is not the remit of this Phase I trial to recruit a sufficient number of participants to be statistically confident about the differences between groups. By the end of this study 6 participants will have been exposed to each schedule in Part 1 (groups A – H) and this provides confidence around the response/event proportions of 0–100% in Table 7.

**Table 7: Sample Size**

Number of “responders”	Proportion if n=6	95% confidence interval 
0	0%	0 – 39%
1	17%	0 – 64%
2	33%	4 – 78%
3	50%	12 – 88%
4	67%	22 – 96%
5	83%	36 – 100%
6	100%	54 – 100%

 Clopper-Pearson method (suitable for small sample sizes)

It is difficult to give an estimate of the power of group comparisons using quantitative antibody titre outcomes at this stage as this is dependent on the number of responders.

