## 7.6 CLINICAL STUDY DESIGN

To identify an effective Ad4 based oral vaccine that promotes systemic and mucosal responses to the HIV-1 envelope glycoprotein, our group will adopt a two part adaptive clinical trial. The study will assist in rapidly screening the impact of different routes, combination regimes and boosting options to Ad4-EnvCN54, MVA-CN54 and CN54gp140 / MPLA, to augment systemic and mucosal antibody responses following initial priming with Ad4.

The study will enrol 48 participants to Part 1 and 12 participants in Part 2. Recruitment will select potential participants who are willing to undergo serial blood draws. Additional participants may be enrolled to replace any early withdrawals.

**In Part 1**, n=6 participants per group will be randomised to groups A-H (Table 1). This design varies the number of Ad4 administrations, from 1 to 3, combined with either CN54gp140 protein boosts (A-D) or co-administration of gp140 with MVA (E-H). Groups A (gp140 alone) and E (MVA-CN54/CN54gp140 alone) will serve as control groups to assess the added benefit of the Ad4 vector. Each vaccine group (A-H) will be assessed for number of mucosal responders (mucosal antibody (rectal/genital/nasal) as measured by ELISA), and titre (mucosal and systemic) of antigen specific binding antibody. Based on data from the MUCOVAC2 study, in which participants received 3 intramuscular doses of CN54gp140 with GLA-AF adjuvant, we anticipate that there will be no mucosal responders in group A (although there will be detectable systemic responses). Enrolment through to completion of the primary immunological assessment for each group will be 7 months.

**In Part 2**, the best regimes from A-D (Ad4-EnvCN54/CN54gp140) and E-H (Ad4-EnvCN54/MVA-CN54/CN54gp140) will be expanded to n=12 (additional n=6) in Part 2. Immune responses at the Primary Immunogenicity Endpoint (Week 26) will be analysed. Selection will be based on total number of responders. In the event that more than one group has the same number of responders, mucosal antibody titre will be used to rank groups to determine which to take forward to Part 2. Should mucosal titers be indistinguishable between groups, then serum antibody levels will be taken into consideration in the selection of groups to progress to Part 2.

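### Protocol Table 7 prints the 95% interval for 0 of 6 as 0–39%, but the Clopper-Pearson method it names gives 0–46%, as its own 6-of-6 row implies

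*Protocol*

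**What the plan says.** Protocol section 14.3 states that the trial is not sized to be confident about differences between groups. It then notes "By the end of this study 6 participants will have been exposed to each schedule in Part 1" and says of that number that "this provides confidence around the response/event proportions of 0–100% in Table 7". After the table it declines to estimate power for titre comparisons.

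Table 7 lists each possible count from 0 to 6 under the column headings "Proportion if n=6" and "95% confidence interval". The footnote names the interval: "Clopper-Pearson method (suitable for small sample sizes". The row for 0 reads 0–39% and the row for 6 reads 54–100%. Nothing marks either row as one-sided or as calculated by another method. The SAP neither repeats nor corrects the table.

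Two other places bear on the zero row. Protocol section 7.6 says "we anticipate that there will be no mucosal responders in group A", and the protocol summary says the same. Section 14.2.1 lists among the primary safety endpoints "Proportion of participants with vaccine-related serious adverse events (SAEs) throughout the study period", which is also a proportion for which zero is a natural count.

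**The concern.** The interval for 0 of 6 does not follow the method in the table's own footnote, and the two extreme rows do not agree with each other. The error runs in the favourable direction: the table shows less uncertainty after a zero count than the named method gives.

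The section offers no power calculation, so Table 7 is all that tells a reader what six participants per group can show. Zero is also the one mucosal responder count that the protocol predicts in advance. A reader using the table to judge what 0 of 6 means, for response or for events, would take the upper limit to be 39% when it is 46%.

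**Working it through.** **Inputs.** n = 6, 95% confidence, Clopper-Pearson, and the seven printed intervals, all from Protocol Table 7. Sidedness is not stated. I take the intervals as two-sided, and the results below bear this out.

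**Formulas.** For x responders of n:
- lower limit = the 0.025 quantile of Beta(x, n − x + 1), or 0 when x = 0
- upper limit = the 0.975 quantile of Beta(x + 1, n − x), or 1 when x = n
- for x = 0 the upper limit reduces to 1 − 0.025^(1/n); for x = n the lower limit reduces to 0.025^(1/n)

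**Recomputing every row.**

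| Responders of 6 | Table 7 | Two-sided 95% Clopper-Pearson | Agrees after rounding |
|---|---|---|---|
| 0 | 0–39% | 0–45.9% | No |
| 1 | 0–64% | 0.4–64.1% | Yes |
| 2 | 4–78% | 4.3–77.7% | Yes |
| 3 | 12–88% | 11.8–88.2% | Yes |
| 4 | 22–96% | 22.3–95.7% | Yes |
| 5 | 36–100% | 35.9–99.6% | Yes |
| 6 | 54–100% | 54.1–100% | Yes |

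For the failing row: 1 − 0.025^(1/6) = 1 − 0.541 = 0.459. The shortfall is 45.9 − 39 = 6.9, or about 7 percentage points.

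**Check that needs no software.** Clopper-Pearson limits are symmetric: the upper limit for x and the lower limit for 6 − x add to 100%. In the printed table:
- 1 and 5: 64 + 36 = 100
- 2 and 4: 78 + 22 = 100 and 96 + 4 = 100
- 3 with itself: 88 + 12 = 100
- 0 and 6: 39 + 54 = 93

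Only the last pair fails. Given the printed 54%, the entry for 0 of 6 has to be 100 − 54 = 46%.

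**What would give 39%.**
- One-sided 95% exact limit: 1 − 0.05^(1/6) = 39.3%
- Mid-p limit, solving 0.5(1 − p)^6 = 0.025: again 1 − 0.05^(1/6) = 39.3%
- Wilson limit, z²/(n + z²) with z = 1.96: 3.84/9.84 = 39.0%

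None of the three explains the whole table, because each would put the 6-of-6 lower limit at about 61% (100 − 39), not 54%. Away from the extremes, Wilson gives 3.0–56.4% for 1 of 6, against the printed 0–64%.

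**What 39% means in probability.** At a true rate of 39%, the chance of 0 of 6 is 0.61^6 = 5.2%. A two-sided 95% limit leaves 2.5% in that tail, which is reached at a true rate of 45.9%.

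**The case against.** The strongest reply is that nothing depends on the cell. No target precision or power determines n = 6. Selection for Part 2 uses responder counts and titres (Protocol sections 7.6 and 10.1.3) or a count above a titre threshold, with serum titres as a fallback (SAP section 3.2), not interval limits. Intervals for reported results will be computed from trial data (Protocol sections 14.5.2 and 14.5.4; SAP sections 12.1 and 12.2.1), so the printed 39% carries into no result. For safety, six per group is not the only denominator. Protocol section 14.5.4 also reports overall, and SAP section 12.2.2 splits Part 1 by arm where possible. With zero events the two-sided upper limit is 1 − 0.025^(1/24) = 14% for 24 per arm and 1 − 0.025^(1/48) = 7% for all 48. All of this stands. It limits the weight of the point but does not make the cell right.

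Three stronger readings are tempting, and the documents do not support them.
- A reader might infer that the zero row is the one the trial leans on most. The documents do not say so; Table 7 is offered for the full range of proportions. They support only that zero mucosal responders is anticipated for group A.
- A reader might infer that the protocol claims it can exclude a true rate of 40% or more after a zero count. It makes no such claim.
- A reader might infer that the table also misstates precision for cervico-vaginal and semen samples, where only one sex contributes. Table 7 is expressly conditional on n = 6. Stratifying by gender fixes no sex ratio, so any smaller denominator would be a guess. The SAP already analyses each mucosal site separately, and its example Table 1.1a has an N row.

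**Conclusion.** The entry is wrong as written. Under the method named, the interval for 0 of 6 is 0–46%, not 0–39%, and the upper limit is understated by 7 percentage points. This rests on one assumption, that the table is two-sided; the six rows that reproduce support it, and the 6-of-6 row settles the value by symmetry. How 39% came about cannot be established, because three different methods give it.

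The point is minor in consequence. It corrects a figure in the only precision statement behind six participants per group. It is not grounds for questioning n, the rules for choosing groups for Part 2, or the planned analyses.

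**What to change.** In Protocol Table 7, change the interval in the 0-responder row from 0–39% to 0–46%. The footnote and the other six rows can stay as they are. If a one-sided 95% limit was intended for the extreme counts, both extreme rows would need that label and would read 0–39% and 61–100%; correcting the single cell is simpler and keeps the table on one method.

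The cost is one table cell. The stated precision for a zero count becomes slightly less favourable, and nothing else in the protocol or SAP needs to change as a result.
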